3.8 Data collection

Schedule of data collection are shown in protocol flow chart and data table, see figure 2, and table 1

3.8.1 Job description of study personnel

Principle investigator will designate a specific job to the research team member. Job description according to each researcher will be clearly specified.

3.8.2 Training study personnel

Research assistants will be trained regarding to good clinical practice guideline, protocol, and collecting the data. Training of performing sleep test, and applying and retrieval of CPAP data will be held at Ramathibodi Hospital Sleep Disorder Center.

3.8.3 Data collection and management

Case record form (CRF) will be developed to collect data regarding baseline demographic data, intervention, primary and secondary endpoints, adherence to interventions, and adverse effect.

3.9 Sample size estimation

3.9.1 Based on primary outcome

Power	Alpha	SD	Mean difference	M (Intervention /control)	Intervention N	Control N	Total N
0.80	0.05	7.4	2.0	1	216	216	432
0.80	0.05	7.4	2.5	1	139	139	278
0.80	0.05	7.4	3.0	1	111	111	222
0.80	0.05	7.4	3.5	1	71	71	142

Sample size calculation will be based on the primary outcome, which is the reduction in blood pressure. Based on the previous data by Reid, et al the mean diastolic blood pressure during pregnancy approximates 92.7 ± 7.4 mmHg [50]. Type I & II error and a ratio of intervention versus control are set at 0.05, 0.2, and 1:1, respectively. Estimated sample sizes are display below according to level of mean differences.

A systematic review and meta-analysis showed that CPAP could reduce blood pressure in OSA patients of -2.87 (95%CI -5.18-0.55) [25]. We, therefore, set mean difference of at least 2.5 mmHg, which will require 278 subjects to enroll. Taking into account for loss to follow-up of 20%, a total of 334 subjects are required (167 each arms). Additional number of subjects to be recruited was increased during January 2019-May 2019 up to 360 cases to allow for the potential subject discontinuation of the study with approval of the ethic committee.

3.9.2 Based on composite endpoint

Sample size calculation is also done according to the composite endpoint.

- **Composite 1 (hypertensive disorder of pregnancy)**

For composite endpoint 1, sample size of 134 each arm is required to detect difference of 15% with type I and II error of 0.05 and 0.20 respectively. Therefore, given the sample size of 153 each arm from the primary endpoints, it is possible to include this composite endpoint.

- **Composite 2 (hypertensive disorder of pregnancy or preterm labor or fetal growth restriction or emergency C/S)**

For composite endpoint 2, sample size of 141 each arm is required to detect the difference of 15% with type I and II error of 0.05 and 0.20 respectively. Therefore, given the sample size of 153 each arm from the primary endpoints, it is possible to include this composite endpoint.

And given the limitation in number of participant enrollment (n=306), estimation of the power of the study based on the effect size of the CPAP on composite endpoint 2 are done below. To achieve a difference of 12% and 15% on the composite endpoint 2, given the sample size of 306, it will achieve the power of 0.83 and 0.97, respectively.

- **Composite 3**

For composite endpoint 3, sample size of 492 each arm is required to detect difference of 6% with type I and II error of 0.05 and 0.20 respectively. Therefore, given the sample size of 153 each arm from the primary endpoints, it is **Not** possible to include this composite endpoint.

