3.7.2 Control Group

- Subjects will receive standard antenatal care and follow-up plan similar to the intervention group.

Primary outcome

- Systolic and diastolic blood pressure, which will be measured at rest using sphygmomanometer twice on both arms by research nurses during daytime ANC at 10:00-12:00 pm at randomization (GA 0-16 week), 1.5-2 month after randomization (GA 18-20 week), and 3-4 month after randomization (GA 24-28 week), 5-6 month after randomization (GA 32-34 week) and monthly (GA>35 week) until delivery

Secondary outcome

- 24-hour ambulatory blood pressure monitoring (daytime versus night time) using the non-invasive technique from pulse transit time (SomnoTouch NIBP).
- Pregnancy complication listed as composite endpoints below

(Composite endpoint): A combination of clinical endpoints in maternal and fetal outcomes, data from Ramathibodi hospital during 2013-2014) *

- **Composite 1:** hypertensive disorder of pregnancy;
- **Composite 2:** hypertensive disorder of pregnancy or preterm labor or fetal growth restriction
- **Composite 3:** Preterm labor or fetal growth restriction, or severe pre-eclampsia or eclampsia or death; (composite 3 incidence=10%)

*Given that the incidence of hypertensive disorder incidence= $136/3787=3.6\%$;
gestational diabetes incidence= $601/3787=15.9\%$; fetal growth restriction incidence= $157/3787=4.1\%$; preterm labor incidence=10%; and severe pre-eclampsia/eclampsia/HELLP syndrome incidence= $(43+ 1+3=46/3787=1.2\%)$, respectively.

- Individual component of the composite endpoints including incidence of hypertensive disorder of pregnancy, gestational diabetes, preterm labor, and fetal growth restriction
- Glucose level, Oral Glucose Tolerance Test (OGTT), HbA1C
- Fetal ultrasound results: uterine Doppler arterial blood flow, fetal growth restriction
- Neonatal outcome: birth-weight, APGAR score, Length of stay, NICU admission

- Placenta character: weight will be measured at birth by the neonatal nurse.

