### **Secondary outcome**

- 24-hour ambulatory blood pressure monitoring (daytime versus night time) using the non-invasive technique from pulse transit time (SomnoTouch NIBP).
- Pregnancy complication listed as composite endpoints below

**(Composite endpoint):** A combination of clinical endpoints in maternal and fetal outcomes, data from Ramathibodi hospital during 2013-2014) \*

- **Composite 1:** hypertensive disorder of pregnancy or gestational diabetes; (composite1 incidence= $699/3787=18.5\%$ )
- **Composite 2:** hypertensive disorder of pregnancy or gestation diabetes or preterm labor or fetal growth restriction (composite 2 incidence = $812/3787= 21.4\%$ )
- **Composite 3:** Preterm labor or fetal growth restriction, or severe pre-eclampsia or eclampsia or death; (composite 3 incidence= $10\%$ )

\*Given that the incidence of hypertensive disorder incidence= $136/3787=3.6\%$ ; gestational diabetes incidence=  $601/3787=15.9\%$ ; fetal growth restriction incidence=  $157/3787=4.1\%$ ; preterm labor incidence= $10\%$ ; and severe pre-eclampsia/eclampsia/HELLP syndrome incidence= ( $43+ 1+3=46/3787=1.2\%$ ), respectively.

- Individual component of the composite endpoints including incidence of hypertensive disorder of pregnancy, gestational diabetes, preterm labor, and fetal growth restriction
- Glucose level, Oral Glucose Tolerance Test (OGTT), HbA1C
- Fetal ultrasound results: uterine Doppler arterial blood flow, fetal growth restriction
- Neonatal outcome: birth-weight, APGAR score, Length of stay, NICU admission
- Placenta character: weight will be measured at birth by the neonatal nurse.

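### The Protocol redefines Composite 1 as hypertensive disorder alone but keeps the sample size and feasibility statement of the former endpoint, so the feasibility claim has no supporting control rate

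*Protocol*

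**What the plan says.** Protocol, list of secondary outcomes under 3.7.2: "Composite 1: hypertensive disorder of pregnancy". No incidence is printed beside it. The footnote begins "Given that the incidence of hypertensive disorder incidence" and gives 136/3787 = 3.6%. The source is described as "data from Ramathibodi hospital during 2013-2014".

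Protocol, 3.10.4: gestational diabetes is one of the inclusion criteria and was dropped from the endpoint analyses.

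Protocol, 3.9.2: under "Composite 1 (hypertensive disorder of pregnancy") the text reads "For composite endpoint 1, sample size of 134 each arm is required to detect difference of 15" per cent, with type I and II errors of 0.05 and 0.20. Because 153 per arm exceeds 134, the section judges that the endpoint can be included.

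Combined protocol and SAP, 3.9.2: the same 134, 15% and conclusion appear. There, however, Composite 1 is "hypertensive disorder of pregnancy or gestational diabetes; (composite1 incidence" 699/3787 = 18.5%).

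Protocol, 3.9.1: the size is now 334 (167 per arm), later raised to as many as 360. The figure of 153 per arm belongs to the total of 306 in the Combined protocol and SAP.

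**The concern.** The label and definition of Composite 1 changed, and the calculation beneath them did not. This is more than a difference between two versions. The inherited number sits in the operative sample-size section of the current Protocol, and that section rests its decision to include the endpoint on it.

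Set beside the only rate the Protocol gives for hypertensive disorder, the planned effect is arithmetically impossible. At stake is how a result on hypertensive disorder is read. Research question 1.2.1 asks about maternal complications, and a null finding could be taken as a negative with 80% power when no stated input supports that. Enrolment itself is not affected, because the trial's size is set by blood pressure in 3.9.1.

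**Working it through.** **Inputs.** Two-sided alpha 0.05 (3.10.4), power 0.80 (3.9.2), allocation 1:1 (3.9.1). Rates are 18.5% for the former Composite 1 and 3.6% for hypertensive disorder. The difference is 15 points.

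**Formula.** With p̄ = (p1 + p2)/2 and d = |p1 − p2|,

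n per arm = [1.96·√(2p̄(1−p̄)) + 0.8416·√(p1(1−p1) + p2(1−p2))]² / d².

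**Step 1: reproduce 134.** For 18.5% against 33.5%, p̄ = 0.26:

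- 1.96·√0.3848 = 1.2158
- 0.8416·√0.37355 = 0.5144
- (1.7302)² / 0.0225 = 133.05, which rounds up to 134. (The unrounded 699/3787 gives 132.91, so 133.)

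A second route exists. For 30% against 15% the formula gives 120.47. The continuity correction, n/4·[1 + √(1 + 4/(n·d))]², gives 133.47, again 134. Neither 33.5% nor 30% is stated anywhere as a rate for hypertensive disorder.

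**Step 2: a true fall from the former rate.** For 18.5% to 3.5%, p̄ = 0.11 and (0.8673 + 0.3616)² / 0.0225 = 67.1, so 68 per arm, not 134.

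**Step 3: the rate now stated.**

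- 3.6% − 15 points = −11.4%, so no sample size exists.
- 3.6% to 18.6% (a rise): 68, or 81 with continuity correction, 65 unpooled, 54 one-sided.
- 15% read as a relative reduction (3.6% to 3.06%): about 17,300 per arm.

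None of these is 134.

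**Step 4: power at 3.6% and 153 per arm.** Expected control events are 153 × 0.036 = 5.5. If CPAP prevented every case, Fisher's test needs at least 6 control events against 0 (p = 0.030; 5 against 0 gives 0.060). Uncorrected chi-square needs at least 4. With X ~ Binomial(153, 0.036), P(X ≥ 6) = 0.47 and P(X ≥ 4) = 0.80. Expected event cells are 5.5/2 ≈ 2.8, so Fisher is the natural choice under 3.10.4. If CPAP halved the rate, exact power is 0.08 (Fisher) or 0.14 (chi-square). At 180 per arm, Fisher power is 0.63 for complete prevention and 0.10 for halving.

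**Step 5: assumed control rates.** The control rates below are assumptions; the documents give none for high-risk women. Same formula, no continuity correction.

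| Assumed control rate | n per arm for a 15-point fall | Relative reduction implied | Smallest fall with 80% power at 153 / 167 / 180 per arm (points) |
|---|---|---|---|
| 15% | complete prevention | 100% | 9.7 / 9.3 / 9.0 |
| 20% | 76 | 75% | 11.2 / 10.8 / 10.5 |
| 30% | 121 | 50% | 13.5 / 13.0 / 12.5 |
| 40% | 152 | 38% | 15.0 / 14.4 / 13.9 |
| 50% | 170 | 30% | 15.8 / 15.1 / 14.6 |

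**The case against.** The strongest reply is that 3.6% was never declared the planning rate. It is a footnote figure from one hospital, and nothing says the 15 points come off it. The trial enrols women with chronic hypertension, hypertension before 20 weeks, earlier pre-eclampsia or gestational hypertension, obesity or diabetes, all with sleep-disordered breathing (3.2.1). Section 2.1 counts chronic hypertension among the hypertensive disorders of pregnancy. The trial's rate should therefore exceed 3.6%. Above 15% and up to about 40%, a 15-point fall has at least 80% power with 153 per arm.

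This stands, and it limits the point. A reader might infer that Composite 1 is hopelessly underpowered in this trial. The documents do not support that, because the low powers in Step 4 hold only at 3.6%. The reply does not rescue the text, however: it relies on a control rate that the Protocol does not state.

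Two other inferences go too far:

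- **That 134 was certainly computed as a rise from 18.5%.** The stated 492 for Composite 3 fits this pattern (10% against 16% gives 491.99). But 21.4% against 36.4% gives 143, not the 141 stated for Composite 2, and 134 also arises from 30% to 15% with continuity correction. The rise is plausible, not demonstrated.
- **That the 3787 records are all deliveries at the hospital.** The text does not say so, and 3.1.1 gives about 3,000 a year. What can be said is that no restriction to high-risk women is stated.

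**Conclusion.** The Composite 1 paragraph in Protocol 3.9.2 is wrong as written. Its 134 per arm, its 15-point difference and its conclusion belong to an endpoint the Protocol no longer uses. The figure cannot be derived from the one incidence stated for the endpoint it does use.

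The feasibility claim is unsupported rather than shown to be false. Whether it holds depends entirely on an unstated control rate. At 3.6% no 15-point fall exists. From 20% to 40% (assumed), 153 per arm is enough. At 50% (assumed), 170 are needed: more than 153 or 167, fewer than 180. These sizes rest on the uncorrected pooled formula, complete data and 1:1 allocation. Whether a 15-point effect is realistic is a separate judgement that these figures do not settle.

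The consequence is confined to a secondary endpoint and its interpretation. It should be corrected, but it does not touch the primary sample size.

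**What to change.** In Protocol 3.9.2, for Composite 1, do one of the following:

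1. **Recompute.** State a control rate for hypertensive disorder in the high-risk women enrolled, with its source, or give a table over an assumed range such as 15% to 50%. Then give the detectable difference at the analysable number per arm, using the current size in 3.9.1 (167 per arm, or up to 180 if 360 are enrolled, less losses) in place of 153.
2. **Remove.** Delete the 134 and the sentence that the endpoint can be included. Label Composite 1 as not formally powered, and report it as a risk difference with its confidence interval.

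In either case, say that the 3.6% hospital figure cannot carry a 15-point reduction. The trial's own event rate pooled over arms should not serve as the planning control rate: it is not a control rate, and it would turn the statement into power calculated after the fact.

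The cost is wording and a short recalculation, with no change to design, conduct or enrolment. The price is that the feasibility statement becomes conditional or is withdrawn.

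### Composite 2's sample size and power figures in section 3.9.2 contradict each other, and the figures for composites 1 and 2 were carried over from definitions that included gestational diabetes

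*Protocol*

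**What the plan says.** Protocol section 3.9.2 sizes three composite endpoints at type I and II errors of 0.05 and 0.20. It states neither event rates nor the direction of effect.

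- Composite 1: "sample size of 134 each arm is required to detect difference of 15" points.
- Composite 2: "sample size of 141 each arm is required to detect the difference of 15" points. A further paragraph gives power for differences of 12 and 15 points: "given the sample size of 306, it will achieve the power of 0.83 and 0.97, respectively".
- Composite 3: "sample size of 492 each arm is required to detect difference of 6" points, judged out of reach.

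For composites 1 and 2 it concludes: "given the sample size of 153 each arm from the primary endpoints, it is possible to include this composite endpoint".

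In 3.9.2 composite 2 is "hypertensive disorder of pregnancy or preterm labor or fetal growth restriction or emergency C/S". In the secondary outcome list under 3.7.2 it is "hypertensive disorder of pregnancy or preterm labor or fetal growth restriction", without emergency caesarean section. Section 3.10.4 says that gestational diabetes was dropped from the endpoint analyses. However, the secondary objective in 1.3.2 still has it in the composite, and 3.7.2 still lists it as an individual component.

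The Combined protocol and SAP, which predates the 2019 recruitment increase recorded in the Protocol, gives the same 134, 141, 0.83 and 0.97. There, composites 1 and 2 included gestational diabetes, with stated rates of 18.5% (699/3787) and 21.4% (812/3787).

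**The concern.** Section 3.9.2 is the only stated support for the claim that the trial is large enough for composites 1 and 2. Two of its figures for composite 2 cannot come from the same pair of rates. In addition, the figures for composites 1 and 2 were produced for definitions that have since lost a component with a hospital rate of 15.9% (601/3787). A reader who wants to know what difference the trial could detect, for example when interpreting a non-significant composite, cannot find out from this section. The unsettled definitions matter beyond planning, because 3.10.4 tests these composites and the components decide who counts as an event.

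**Working it through.** **Inputs.** Two-sided α = 0.05 (3.10.4), 80% power (3.9.2), 1:1 allocation (3.9.1). The stated n, power and 153 per arm are from Protocol 3.9.2. The rates 18.5% and 21.4% are from the Combined protocol and SAP, secondary outcome section, and are used only to trace where the figures came from. Component rates are from Protocol 3.7.2.

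**Formulas** (pooled two-proportion test, no continuity correction, p̄ = mean of p₁ and p₂):

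- n per arm = [1.960·√(2p̄(1−p̄)) + 0.842·√(p₁(1−p₁)+p₂(1−p₂))]² / (p₁−p₂)²
- power = Φ{[|p₁−p₂|·√n − 1.960·√(2p̄(1−p̄))] / √(p₁(1−p₁)+p₂(1−p₂))}

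**1. Reproduce the stated powers.** At 153 per arm:

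- 21.4% to 6.4%: (0.15 × 12.369 − 1.960 × √0.2394)/√0.2281 = 1.877, power 0.970.
- 21.4% to 9.4%: (0.12 × 12.369 − 1.960 × √0.2606)/√0.2534 = 0.961, power 0.832.

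Both match the plan's 0.97 and 0.83.

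**2. Reproduce 141.**

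| Rates | Difference | n per arm |
|---|---|---|
| 21.4% to 9.4% | 12-point fall | 140.8 |
| 21.0% vs 36.0% | 15 points | 141.0 |
| 21.4% vs 36.4% | 15 points | 142.2 |
| 21.4% to 6.4% | 15-point fall | 82.3 (83) |

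So 141 is either the n for a 12-point fall from 21.4%, or the n for 15 points at rates near 21% and 36%. On the rates behind the stated powers, 15 points needs 83 per arm.

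**3. The contradiction, without assuming rates.** If 141 per arm gives 80% power, 153 per arm gives about Φ[(1.960 + 0.842) × √(153/141) − 1.960] = Φ(0.958) = 0.83. Reaching 0.97 would take about 141 × [(1.960 + 1.881)/(1.960 + 0.842)]² = 265 per arm. For 12 points at 153 per arm on this basis, power is 0.631 (36% vs 24%) to 0.658 (33% vs 21%), not 0.83.

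**4. Rates for the composites as now defined.**

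- Composite 2 without emergency caesarean: preterm labor 10%, fetal growth restriction 4.1%, hypertensive disorder 3.6%. With full overlap the hospital-wide rate is 10%. With none it is 10 + 4.1 + 3.6 = 17.7%. At 10%, falls of 12 or 15 points are impossible. At 17.7%, 15 points needs 63 per arm and 12 points needs 112.
- Composite 1 is now hypertensive disorder alone. Its only stated rate is 136/3787 = 3.6%, and a 15-point fall from that is impossible.

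**5. The per-arm number.** The 153 per arm (306) is the total from the Combined protocol and SAP. Protocol 3.9.1 now gives 334 (167 per arm), raised to as many as 360 (180 per arm), around a requirement of 278 before loss (139 per arm).

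**6. Illustration with assumed control rates.** Detectable fall at 80% power, in points:

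| Evaluable per arm | 20% | 30% | 40% |
|---|---|---|---|
| 139 (278 in 3.9.1) | 11.7 | 14.1 | 15.6 |
| 144 (360 less 20%) | 11.5 | 13.9 | 15.4 |
| 180 (360, no loss) | 10.4 | 12.5 | 13.8 |

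The three rates are assumptions. The documents give none for the enrolled women.

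**7. Side note on direction (inference).** Composite 1's 134 matches 18.5% vs 33.5% (133.05, rounded up), and composite 3's 492 matches 10% vs 16% (492.0). Both are increases, whereas section 1.2 asks about a reduction. Falls of the same size would need 68 per arm (18.5% to 3.5%) and 283 per arm (10% to 4%).

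**The case against.** The strongest reply is that nothing practical turns on the clash. At 153 per arm, power for 15 points is 0.83 if 141 is right and 0.97 if the powers are right. If the difference beside 141 should read 12 points, 153 still exceeds 141. This stands. A reader might infer that composite 2 is underpowered, or that calling its inclusion possible is wrong, but the contradiction alone shows neither.

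It is also fair to say that 3.9.2 does not control what is analysed: composite 3 is called not possible, yet 3.7.2 and 3.10.4 keep it. The composites are secondary, the trial is sized on blood pressure, and revised planning figures would not change enrolment. That limits the weight of the point but does not make the figures right.

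A reader might further infer from the 3.6% that a 15-point fall in composite 1 cannot happen in this trial. The documents do not support that. The 3.6% is hospital-wide, while 3.2.1 enrols women with hypertension, previous pre-eclampsia, obesity or diabetes, and 2.1 counts chronic hypertension as a hypertensive disorder of pregnancy. Their rate may be much higher. What can be said is that no rate is given on which 134 could rest.

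Lastly, the match of 134 and 492 to increases might be read as proof that the calculations ran in the wrong direction. Section 3.9.2 states neither rates nor direction, and 141 also fits a 12-point fall, so this remains inference. The 12-point reading does not rescue 134, since 18.5% to 6.5% needs 119. Composite 3 is underpowered either way: even for a 6-point fall from 10%, power is 0.54 at 153 per arm and 0.61 at 180.

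**Conclusion.** The point holds in two parts. First, composite 2's own figures are incompatible: 141 per arm for 15 points implies power of about 0.83 at 153 per arm (0.63 to 0.66 for 12 points), against the stated 0.97 and 0.83, while the stated powers imply 83 per arm for 15 points. Which figure is wrong cannot be determined from the documents. Second, and more important, 134, 141, 0.83 and 0.97 belong to composites that included gestational diabetes. As now defined, composite 2 has no stated control rate, only a hospital-wide range of 10% to 17.7% built from its components without emergency caesarean. Composite 1 has only a hospital-wide 3.6%. The stated sample sizes for both are therefore unsupported, which is not the same as shown to be too small. The figures rest on the pooled two-proportion formula with a two-sided 0.05 level. The primary sizing in 3.9.1 is not touched. The analysis is touched only through the unsettled definitions of the composites.

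**What to change.** 1. Settle one definition of each composite and use it in Protocol sections 1.3.2, 3.7.2, 3.9.2 and 3.10.4, stating whether gestational diabetes and emergency caesarean section are in or out.
2. For each composite, state one control rate for the enrolled high-risk population, sourced or labelled as an assumption, and the direction of effect.
3. From that rate, recompute n and power, or the detectable difference at 80% power, at the current per-arm number net of a stated loss. Both 153 and 167 are numbers before loss.
4. Replace 134, 141, 0.83 and 0.97. If 141 was the 12-point figure, correct the difference printed beside it.
5. Keep or revise the statements that composites 1 and 2 can be included according to the recomputed values. If a 6-point fall from 10% is meant for composite 3, restate its n as 283 per arm and say that it remains underpowered.

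The cost is rewriting one section and aligning the definitions. It needs no extra participants and no change to the primary analysis. The stated power may become less favourable.
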